7. STUDY POPULATION AND RECRUITMENT

Study Population

58 older adult men and women of all races and ethnic backgrounds between the ages of 60-90 years with cognitive scores indicative of mild cognitive impairment that includes impaired memory function (i.e., "amnestic MCI or "aMCI") will serve as subjects for this study. To account for a 25% subject exclusion rate due to dropout/experimental failure, failed screening or conversion to dementia (15 subjects), a total of 73 patients with aMCI (~20 subjects/year over 4 years) will be recruited for this study in order to meet our enrollment goal.

Recruitment and Screening

Participants for this study will be recruited through the "Screening eligibility of older adults to participate in clinical trials related to memory" study (UD IRB #1318668), which is being conducted by [name] and [name]. Participants will be primarily recruited through posted flyers and direct mailings targeted towards older adults with a self-report of memory complaints. Additional subjects will be recruited through the Swank Memory Center for Memory Care and Geriatric Consultation ("Swank Memory Center") in Wilmington, DE in collaboration with co-investigator, [name]. Specific details regarding subject recruitment are described in the screening protocol. Briefly, subjects will undergo a brief modified telephone pre-screening for cognitive status (TICS-m) and those qualified will undergo a more comprehensive in person cognitive evaluation with a research nurse. Individuals with memory scores indicative of amnestic MCI that express interest in participating in this study will be recruited for enrollment into this clinical trial by the study coordinator. Additionally, this study will be listed on the Alzheimer's Prevention Registry.

Final eligibility will be determined by the PI based on the inclusion/exclusion criteria stated below:

Inclusion Criteria

- Cognitive function scores consistent with amnestic mild cognitive impairment based on prescreening evaluation;
- age 60-90 years;
- MMSE score >21 at time of initial consent;

Exclusion Criteria

- blood chemistries indicative of abnormal renal, liver, thyroid and adrenal function; estimated glomerular filtration rate using the MDRD prediction equation must be ≥30 ml/min/1.73 m²;
- any clinically significant abnormal blood chemistry values as determined by the NMPCC nurse practitioner;
- major psychiatric disorder (e.g. schizophrenia, bipolar disorder, major depression within past two years);

- neurological or autoimmune conditions affecting cognition (e.g. Parkinson's disease, epilepsy, multiple sclerosis, mild or severe traumatic brain injury, large vessel infarct);
- concussion within last 2 years and ≥ 3 lifetime concussions;
- current systemic medical illnesses, not including diabetes (e.g. cardiovascular disease, cancer, renal failure);
- prior history of any type of cancer other than basal cell carcinoma;
- substance abuse or dependence (DSM-V criteria);
- current use of medications used to treat dementia (e.g., anticholinesterase drugs) or other drugs likely to affect cognition (e.g., anticholinergic drugs, long-acting benzodiazepines);
- claustrophobia, metal implants, pacemaker or other factors affecting feasibility and/or safety of MRI scanning*;
- current smoking (including marijuana) within the past 3 months;
- hospitalization as a result of COVID-19.
- History of heart palpitations or arrhythmias

* In order to protect the health and safety of the participants, exclusion criteria for this study will include any contraindication to magnetic resonance scanning (e.g., metal in body, claustrophobia, pregnant). These exclusions are specific to MRI and are consistent with most studies involving MRI. Potential participants will be screened for the presence of any of these exclusion criteria prior to participating in this MRI study and before each MRI visit by having subjects complete an MRI screening form. **Describe what (if any) conditions will result in PI termination of subject participation.**

The primary exit criteria will include:

- completion of the study;
- failure to comply with the requirements of the study;
- lack of ability to continue to provide consent during the study;
- development of dementia during the study;
- treatment for impaired cognitive function by PCP;
- change in medication status that my affect primary outcomes (as determined by the PI);
- any serious adverse event that results in unblinding, prolonged disruption of the intervention or is deemed unsafe for the participant to continue in the trial.

Other exit criteria will include cardiovascular or metabolic disease-related events (e.g., myocardial ischemia/angina, myocardial infarction, stroke, congestive heart failure, hyperglycemia, etc.), major surgery and other serious changes in health status. Subjects will also have the option of withdrawing from the study at any time for any reason. The number of subjects exiting the study and the reasons for exit will be carefully documented. Subjects who withdraw from the study will be replaced in order to achieve the sample size required for appropriate statistical power.

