- **Middle Cerebral Artery Screening:** A research team member will use a transcranial doppler ultrasound probe to examine the temporal window for screening of a visible middle cerebral artery. This is done during the screening visit to simplify the preparation of Visits 2 & 7. The results of this screening test will not impact eligibility for this study.

RANDOMIZĂTION (will occur after VISIT 1.1)

Randomization Procedures. Subjects who qualify for the study based on screening assessments will be randomly assigned by the study coordinator to receive either treatment A or treatment B. The identity of each treatment (i.e., NR or placebo) will be blinded by the manufacturer (ChromaDex, Inc.) and the blinding code will be sent to a member of the PI's department ([name]) who is unaffiliated with this study. [name] will enter the blinding code in a secure REDCap form that will remain hidden from the rest of the study team. The PI will be given a separate login ID and password to access this REDCap form and determine the assigned treatment condition of a subject in the event of an emergency (described below under serious adverse events). A blocked randomization scheme will be uploaded into REDCap by the biostatistician with block size (*b*) resulting in an imbalance of no more than 2 subjects (*b*/2) between group assignments. To address potential imbalance between key biological variables including sex (male vs. female) and APOEε4 status (carriers vs. non-carriers),

the blocked randomization scheme will be stratified such that participants within each strata will be block randomized to either placebo or NR.

Study Restrictions. All experimental visits will be conducted under overnight fasted conditions (no meal within ~12 hours of testing) with the exception of cognitive function and MRI sessions. Participants will be asked to discontinue use of any vitamin B₃-containing supplements (i.e., nicotinamide, niacin, nicotinic acid, nicotinamide riboside, nicotinamide mononucleotide) 2 weeks prior to and throughout participation in the study. Subjects will be asked to refrain from non-prescription medications for 48 hours; alcohol and exercise for 24 hours, caffeine for 12 hours prior to all study visits as these are factors known to modulate vascular function as well as circulating biomarkers of interest. If subjects receive the COVID-19 vaccine, they will not perform any experimental visit until at least one week following vaccination.

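### The exit criteria end study participation, not only study capsules, so week-12 outcomes that could be obtained are not planned and the comparison becomes one among those who stayed

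*Combined protocol and SAP*

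**What the plan says.** The exit list in section 7 (Study Population and Recruitment) answers a form question about what "conditions will result in PI termination of subject participation". It therefore concerns the study as a whole, not only the capsules. Apart from study completion and the cognitive-decline items (loss of capacity to consent, dementia, treatment for impaired cognition), it includes:

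- "failure to comply with the requirements of the study", with no threshold;
- "change in medication status that my affect primary outcomes (as determined by the PI", with no drug list or criteria;
- "any serious adverse event that results in unblinding, prolonged disruption of the intervention or is deemed unsafe for the participant to continue in the trial".

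The next paragraph begins "Other exit criteria will include cardiovascular or metabolic disease-related events" and adds major surgery and other serious changes in health. It then states: "Subjects who withdraw from the study will be replaced in order to achieve the sample size required for appropriate statistical power". The number of exits and the reasons for them are to be documented.

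Section 6 (Adverse Event Recording) ends event recording when testing is complete or the participant is withdrawn. Section 10 (Data) regresses the change from baseline to week 12 on treatment, adds block indicators as appropriate, and assumes data missing at random or completely at random. It names blood pressure/arterial stiffness and brain blood flow as secondary outcomes, tested at 0.0125.

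On medicines, Study Restrictions in section 6 states "Subjects will be asked to refrain from non-prescription medications for 48 hours", giving effects on vascular function and biomarkers as the reason. The check-ins described for Visits 5 and 6 consist of a symptom survey and PROMIS questionnaires.

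**The concern.** Stopping capsules and leaving the study are different events, and the protocol treats them as one. A participant who takes capsules irregularly, starts a new medicine, or has treatment interrupted after a serious adverse event may still be able to sit the memory tests at week 12. Nothing in the plan asks for that. Because the analysis variable is a change to week 12, a participant with no week-12 value contributes nothing.

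These exits occur after randomisation and for reasons that treatment may influence. Adding new recruits until the target is reached keeps the sample size. The people compared are nevertheless a selected group: those who complied, had no such event, and had no medication change judged relevant. What is at stake is whether the primary cognitive result can be read as the effect of assignment to NR.

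Exits for dementia or lost capacity to consent are outside this point.

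**Working it through.** **1. The plan's own figure.** Section 7 sets a target of 58 and allows 25% for losses: 58 × 0.25 = 14.5, rounded up to 15, and 58 + 15 = 73, as stated. The 25% mixes dropout or experimental failure, failed screening and conversion to dementia. It gives no rate of exit after randomisation, still less one by arm, so exit rates below are assumptions. Whether 73 is enough is a separate matter.

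**2. Is follow-up after exit provided anywhere?**

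| Place | Content | Follow-up after exit? |
|---|---|---|
| Section 7, exit criteria | Ends participation | No |
| Section 7, replacement sentence | Adds new participants | No |
| Section 6, Adverse Event Recording | Ends at withdrawal | No |
| Section 9, Compensation | Pays for visits completed before withdrawal | No |
| Section 10, analysis | Change to week 12; no analysis set defined | No |
| Section 8, MRI risks | Those not completing MRI may continue in the trial | Yes, but for MRI only |

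The MRI provision shows that the protocol can separate one procedure from participation. It does not do so for capsules. In addition, pills are counted at the last post-intervention visit (section 6, Monitoring Adherence), when most or all week-12 data exist. Nothing says whether the data of someone found non-compliant at that point are kept.

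**3. Size of the bias.** In each arm let p be the share who exit and g the amount by which exits would have scored worse than stayers at week 12, with the same g in both arms. The arm mean is (1 − p) × stayer mean + p × exit mean, so the stayer mean equals the arm mean + p × g. Hence

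bias in the NR − placebo difference = (p_NR − p_placebo) × g.

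Assumed inputs: p_NR = 0.15, p_placebo = 0.05, g = 0.5 to 1.0 SD.

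- 0.10 × 0.5 SD = 0.05 SD
- 0.10 × 1.0 SD = 0.10 SD

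With more exits on NR this flatters NR; with the shares reversed it counts against NR. For scale, with 58/2 = 29 per arm (equal allocation assumed) the standard error is √(2/29) = 0.26 SD. At 29 per arm, 15% and 5% are about 4 people and 1 to 2 people.

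**4. Does replacement remove it?** A simulation used no true effect, recruitment continued to 29 completers per arm, exit correlated ρ with the week-12 change, and a two-sided 0.05 test (the plan does not state sidedness).

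| Exit shares, arm 1 / arm 2 | ρ | Bias (SD) | Type I error |
|---|---|---|---|
| 20% / 20% | 0 to 0.6 | 0.000 to 0.003 | 0.048 to 0.052 |
| 25% / 15% | 0 | −0.001 | 0.051 |
| 25% / 15% | 0.3 | 0.045 | 0.055 |
| 25% / 15% | 0.6 | 0.092 | 0.067 |
| 30% / 10% | 0 | 0.002 | 0.050 |
| 30% / 10% | 0.3 | 0.090 | 0.063 |
| 30% / 10% | 0.6 | 0.182 | 0.113 |

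Replacement keeps 29 per arm in every row, and the bias remains wherever exits are both unequal and related to outcome. It vanishes when either condition fails.

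**The case against.** The best defence is in section 10: the sponsor expects treatment not to influence continuation, on the basis of its pilot, and states that a linear model is valid under missingness at random. Exit reasons are documented, and the illustrated bias is small beside a standard error of 0.26 SD. The point about size stands. The modelling defence stands only in part. The model described contains treatment and block, so stayers give a valid answer only if exit is unrelated to week-12 change given those. Non-compliance, new medicines and serious adverse events are not in the model. Documenting reasons helps reporting but recovers no outcomes.

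Several stronger readings are tempting, and the documents do not support them.

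- *Any capsule interruption or any unblinding ends participation.* Each is a named trigger only through a serious adverse event, and the disruption must be prolonged. Section 8 handles missed doses within the study, although the open-ended non-compliance item could catch some interruptions.
- *Collected data are thrown away.* No passage says so. Later data are not planned, and the plan is silent on data already in hand.
- *Replacement of people terminated by the PI is explicit.* The sentence covers those who withdraw, and section 9 distinguishes withdrawing from being withdrawn. Including both is the natural reading, since the aim is to reach the sample size, but it is implied.
- *The PI's access to the blinding code taints the medication judgement.* Section 6 limits that access to emergencies and blinds those acquiring or analysing data.
- *Changes in blood-pressure medicines escape every rule and cannot be seen.* The protocol's own hypothesis links blood pressure to memory, so the PI could judge such a change relevant. The APOE paragraph in section 6 calls cardiovascular outcomes primary, and adverse-event records include treatment. As worded, the plan otherwise keeps these participants, which is what one would want. What remains is that the described check-ins do not ask about prescription changes and section 10 plans no sensitivity analysis for them.

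**Conclusion.** The concern holds in this limited form. The plan ends participation for events after randomisation, provides no week-12 assessment after them, and does not state that everyone randomised is analysed in the assigned arm. The comparison is then one among stayers, and replacement does not repair that.

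The size is uncertain and probably modest: 0.05 to 0.10 SD under assumed exits of 15% versus 5% and a gap of 0.5 to 1.0 SD, or about a fifth to two fifths of the standard error (0.05/0.26 and 0.10/0.26). The most extreme simulated setting gives 0.18 SD and a type I error of 0.113. None of the exit rates, gaps or correlations comes from the documents. The case for change rests on low cost and an avoidable loss of information in a trial of 58, not on evidence that serious bias will occur. The medication point is minor and concerns recording and a sensitivity analysis only.

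**What to change.** Leave unchanged when capsules are stopped and every safety rule. Add to section 7 that a randomised participant who stops capsules or meets one of these criteria, and who still consents and can be tested safely, is asked to complete Visits 7-9, with the event and its date recorded. Add to section 10 that the main analysis includes such participants in their randomised arm, whatever capsules were taken. Reword the replacement sentence so that added recruits are additional participants and do not substitute for anyone in the analysis. State whether it covers people who are withdrawn as well as those who withdraw.

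As a minor addition, ask about prescription-medicine changes at the existing check-ins. Keep participants whose vasoactive medicines changed in the main analysis of the secondary vascular outcomes, and add a sensitivity analysis that leaves them out. That analysis selects on an event after randomisation, so it should stay secondary.

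Cost: protocol wording, one check-in question, and week-12 visits for a few participants on top of those for added recruits. Because the estimate will include people off treatment, it may be slightly diluted. This does change what the exit criteria mean for follow-up, so the consent form and the compensation text in section 9 should be brought into line.

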8. RISKS AND BENEFITS

List all potential physical, psychological, social, financial or legal risks to subjects (risks listed here should be included on the consent form).

• Nicotinamide Riboside (NR) and Placebo Capsules - Subjects will either be given nicotinamide riboside (NR) capsules (Niagen®; 500 mg 2x/day) to raise blood levels of NAD+, or placebo capsules that contain inactive ingredients (microcrystalline cellulose within vegetarian capsule). Potential side effects associated with NR may include mild-to-moderate cases of headache, feelings of warmth, hot flushing sensations, gastrointestinal discomfort, and fatigue. There are currently no reports of serious adverse side-effects to NR supplementation; however, all adverse events will be closely monitored. To lessen the risk of side effects, subjects will take capsules twice a day instead of all at once. If they miss a dose, subjects will be instructed not to double the number of capsules that they take and to just take the next dose at the regularly scheduled time. If subjects are allergic to or have had an adverse event after taking one of the abovementioned drugs or supplements, they will be asked to notify the investigator before participating.

Per Niacin's FDA label, cardiac arrhythmias and palpitations have been reported during Niacin use. Niacin is a closely related compound to nicotinamide riboside. There are ongoing clinical trials using the current compound, nicotinamide riboside, as an intervention for preventing atrial fibrillation in people with heart failure; thus, the actual risks of cardiac arrhythmias with NR are unknown.

- Blood Draw When the needle goes into a vein, it hurts for a short time and there may be redness or swelling around where the needle goes into the skin. There is a small chance you may feel lightheaded or faint. In about 1 in 10 cases, a small amount of bleeding under the skin will cause a bruise. A risk of a blood clot forming in the vein is about 1 in 100. The risk of infection or significant blood loss is less than 1 in 1,000. The total amount of blood being drawn over the entire study is approximately 9.0 tablespoons (less than 1/3 pint). Subjects should not donate blood 8 weeks before or after taking part in this study.
- Genetic Risk for AD One of the blood tests will determine whether or not the subject carries a gene that has been associated with risk for Alzheimer's disease (AD). People with this gene have a higher chance of developing AD compared with people who do not carry the gene. Some people who carry the gene may never develop AD. Others may develop AD even though they do not carry the gene. Subjects will be provided with the results of this test upon request only.
- Cerebrovascular Function There are no risks associated with breathing slightly higher or lower amounts of carbon dioxide. The use of CO₂ to manipulate brain blood flow in humans has been applied clinically and in the research setting for decades without any adverse events. Subjects may feel an increase in heart rate, flushed skin, and minor disorientation or slight metallic taste while breathing the carbon dioxide mixture. A mild headache is also possible. Subjects may experience a dry mouth due to the use of the facemask during the test.
- MRI Scan MRI is an imaging technique that uses radio waves and magnetic fields to produce images of internal structures in your body. Unlike X-rays, the MRI does not use any ionizing radiation, and it does not use radioactivity, so there is no radiation related risks from having an MRI scan done on you. Below there is a description of MRI related risks and what is being done to reduce any possible risks associated with them:
 - Metal: The MRI scanner produces a constant strong magnetic field, which may cause any metal implants, clips, or implanted medical devices within your body to shift position or malfunction. You will not be allowed to participate in this study if you have any implanted metal, clips or devices. You will be screened to make sure that it is safe for you to enter a strong magnetic field. Please provide us with as much information as you can, for example if you had surgery in the past, so that we may decide whether it is safe for you to be a participant. Metallic objects brought into the MRI environment can become hazardous projectiles and can also interfere with the data quality. To minimize this risk, metal earrings, other piercings, necklaces and any other metal in contact with your body must be removed prior to the study. You must also remove all items from your pockets, including coins, electronics (including cell phones and hearing aids) and wallets. You must remove belts with metal buckles, and you may be asked to change into a gown that we will provide if your clothing contains significant metal, including metal underwire bras.
 - Inner ear damage: MRI scanning produces loud noises that can cause damage to the inner ear if appropriate hearing protection is not used. Earplugs and/or headphones will be provided to protect your ears.
 - Claustrophobia: When inside the MRI scanner, the "bore" of the scanner will surround the part of the body that is being scanned. In the case of fMRI, we are interested in brain activity, and the head will be centered inside a close-fitting scanning coil positioned in the bore of the scanner. If the subject feels anxious in confined, spaces they may not want to participate. If they are unsure, they can try the "mock" scanner at the MRI facility to evaluate their comfort level with the enclosed space of the magnet bore. If they decide to participate and begin to feel claustrophobic, they will be able to communicate with the research team via the intercom or the squeeze ball and the test will be discontinued.

Subjects who do not complete MRI testing will still be allowed to continue with the trial.

- Burns: In rare cases, contact with the MRI transmitting and receiving coil, conductive materials such as wires or other metallic objects, or skin-to-skin contact that forms conductive loops may result in excessive heating and burns during the experiment. The operators of the MRI scanner will take steps, such as using foam pads when necessary, to minimize this risk. Tattoos with metallic inks can also potentially cause burns. In addition, please let the MRI operator know immediately if you experience any heating or burning sensations during a scan. The scanning session will be stopped as soon as you tell the operator.
- Nerve or muscle stimulation. While the scanner is operating, there is a small chance that the rapidly changing magnetic fields could cause a slight tingling sensation or a muscle twitch, usually felt in the upper arms or torso. While these sensations may be startling, they are not dangerous or a health risk, and they have no lasting consequences. The sensations should stop when the scan ends. Because these sensations may nevertheless be distracting or even possibly uncomfortable, please squeeze the signal bulb to alert the scanner operator if you feel tingling or muscle twitching, and we will immediately stop the scan. You will then have the opportunity to choose to withdraw from the study or to continue.
- **Other Risks**. Besides the risks listed above, there are no other known risks from the magnetic field or radio waves at this time. Although functional MRI scanning has been used for more than 20 years, long-term effects are unknown.

There are no alternative methods that would provide the same type and accuracy of information as the state-of-the-art procedures proposed in this application.

In your opinion, are risks listed above minimal* or more than minimal? If more than minimal, please justify why risks are reasonable in relation to anticipated direct or future benefits. (*Minimal risk means the probability and magnitude of harm or discomfort anticipated in the research are not greater than those ordinarily encountered in daily life or during the performance of routine physical or psychological examinations or tests)

The risks associated with this research are minimal and not greater than those encountered during the performance of routine physical or psychological examinations.

What steps will be taken to minimize risks?

Management of general risks of the proposed study:

- Having only qualified and experienced personnel perform the procedures;
- Using only safe, well-established procedures;
- Constant monitoring of the subjects by the members of the investigative team;
- Instating appropriate clinical supervision, availability of emergency equipment and medications (with well-planned emergency procedures), and the overall safety procedures in place within the STAR Health Sciences Complex;
- Establishing a Data and Safety Monitoring Committee to periodically review and evaluate adverse events related to study procedures and/or treatments.

Management of **specific risks** related to drugs/supplements:

- screening for adverse events and allergies to drugs;
- obtaining Investigational New Drug (IND) approval from the FDA;
- working collaboratively with ChromaDex, Inc. and the FDA to ensure that the NR and placebo pills meet all regulatory and safety guidelines, and that there is continuing effective information sharing;

• using a dose of NR therapy that is based on my pilot study, has been shown to have efficacy, but does not result in adverse side effects in human subjects.

Management of **specific risks** related to the collection of MRI data:

- This protocol will be performed using an MR scanner employing pulse sequences and hardware that have been approved by the FDA for human clinical use. The field strength is 3 Tesla and all relevant operating characteristics (RF power deposition, rate of change of the field gradients, coil design) fall within the limits of FDA guidelines for NMR exposure. Participants will be carefully screened to exclude those who may have metal in or on their bodies that cannot be removed (e g., bullets, metal filings, body piercings, etc.). MR Facility rules strictly forbid staff from entering the magnet room carrying metal objects. The risk of claustrophobia is minimized by screening subjects for self-reported claustrophobia and making sure the subject is lying comfortably with head and neck supported and providing ear protection with headphones, a mirror to see out, a button to signal distress, and an intercom. Scan time will be kept to a minimum. If they are unsure about whether or not they may be pregnant, female participants will be given the opportunity to complete a urine pregnancy test immediately before the scanning period, and those with a positive result will not be scanned. With regard to PNS, participants are given a squeeze ball to use in case of an emergency. They are informed that if they experience PNS related sensations or are otherwise uncomfortable, they can alert the MRI technologist via the squeeze ball and the technologist will stop the scan immediately.
- All information obtained during the study will be held in strict confidence to the fullest extent
 possible by law. In no case will a participant's personal identifiable information be shared with any
 other individuals or groups without their expressed written consent. MR Images will be stored on
 secured computer servers and will be archived indefinitely. Non-identifiable images of MR scans
 may be used for teaching purposes, be presented at meetings, published, and also shared in
 databases accessible to other researchers for further research and educational purposes. The
 name or other identifying information associated with the participant will not be used in any
 publication or teaching materials without their specific permission.

Describe any potential direct benefits to participants.

There may be no direct benefit to subjects participating in this research study; however, subjects will receive the results of their screening assessments (i.e., blood glucose status, plasma lipids and lipoprotein profile, blood pressure, blood chemistries). These results will not be interpreted but are provided for information. Subjects will be encouraged to discuss their results with their PCP. **Describe any potential future benefits to this class of participants, others, or society.**

The findings from the proposed research should provide important new information regarding the influence of NR supplementation upon multiple domains of physiological function including vascular, cognitive and neuronal function in older adults with aMCI. In addition, the proposed research should provide important insight into a potential mechanism involved in the modulation of cerebrovascular function with NR (i.e. oxidative stress). Together, this information will contribute to the knowledge of how to prevent and treat cerebrovascular and cognitive dysfunction in older adults with aMCI and possibly lead to future insight into reducing Alzheimer's disease risk.

If there is a Data Monitoring Committee (DMC) in place for this project, please describe when and how often it meets.

This protocol has been reviewed and approved by a Data and Safety Monitoring Board (DSMB) which will convene every 6 months to monitor patient safety, data quality and evaluate study progress. A copy of the DSMB charter as approved by the DSMB is attached with this protocol.

